### 3.4 Blinding, Randomization, and Bias

Eligible subjects who complete the  $14 \pm 3$  day run-in period and meet all study inclusion/exclusion requirements will be randomized in a 1:1 ratio to receive EGT0001442 20 mg/day or placebo according to a computer-generated randomization schedule. Subjects will be assigned to treatment groups in sequential order as they qualify for the study, using a centrally located and managed interactive web response system (IWRS). Randomization will be stratified by study center and screening HbA1c ( $\geq 7$  to < 8.5% or  $\geq 8.5$  to 10%). The study will be conducted at multiple investigative sites and will likely involve variable numbers of subjects at each site. Enrollment will be on a competitive basis but each site will be capped at 15% of the total randomized subjects (45 subjects).

The study drug will be blinded to the sponsor, investigators, study coordinators, pharmacists, study subjects, and the cardiovascular adjudication committee members. Upon randomization, each subject will receive a subject randomization number and drug kit(s) assigned to the subject. To maintain blinding of the treatment, the values of the HbA1c after dosing starts will remain blinded to all study personnel and subjects until all subjects have completed the 24 week treatment period. After all subjects have completed the 24 week treatment period, all previous and subsequent HbA1c values will be made available to the sponsor, investigators, study coordinators, pharmacists, and the study subjects for close monitoring of subjects' safety including assessment of providing rescue medication. Subjects' treatment assignment will continue to be held from all study personnel so the remainder of the study can be conducted in a blinded fashion.

If knowledge of the test substance is needed to manage the subject's condition, the investigator will contact the IWRS to obtain the treatment assignment. If unblinding occurs for any reason, the time and reason for unblinding will be recorded on the case report form (CRF) and the sponsor must be notified within 24 hours.

A designated statistician who is not involved with the study operation will hold the treatment code. The unblinded treatment information can be provided to the DSMB to facilitate the evaluation of any clinically important increase in the rate of a serious suspected adverse reaction or to the designated safety contact when the treatment information is required to determine if an expedited safety report must be submitted to regulatory agencies.

The treatment code will be unblinded after all subjects have completed the planned 96 weeks of blinded study treatment and the subsequent follow-up phase, and the clinical database has been locked

The treatment assignment will continue to be withheld from the cardiovascular adjudication committee members at the conclusion of the study until all phase 2 and 3 investigational studies are completed and a meta-analysis to assess cardiovascular risk is conducted.

### 3.5 Sample Size Justification

Approximately 300 subjects will be enrolled and equitably allocated to receive either EGT0001442 20 mg capsules or placebo.

The sample size of 150 subjects per group was calculated based on the following assumptions:

- The mean change from baseline to Week 24 in HbA1c in the active dose group will be approximately -0.4%.
- The placebo group will not experience a substantive mean change in HbA1c from baseline to week 24.
- The standard deviation of this change is the same for both groups and is 1.0%.
- The two groups are independent, the study design is balanced, and the two-sided significance level for the hypothesis is 0.05.

Under the above assumptions, an evaluable sample size of 133 evaluable subjects per treatment arm yields approximately 90% power that EGT0001442 treatment will be found to be significantly different from placebo. A sample size of 150 subjects per treatment arm will be enrolled to account for any subject lost-to-follow-up.

#### 3.6 PLANNED ANALYSES

Tests of programming and statistical analyses will commence after data have been collected and are available in the database. This initial testing phase will be performed using dummy treatment codes to maintain the treatment blind.

### 3.6.1 Week 24 Analysis

A limited unblinded analysis will be performed after all subjects have achieved the Week 24 primary efficacy endpoint (at the Week 24 visit), after all subject data up to Week 24 have been cleaned and locked. The purpose of the analysis will be to support management decisions about continuing the EGT0001142 development program. The unblinded results will be provided to a limited number of recipients at Theracos, and will not be made available to any other personnel involved in the study conduct. Subjects will continue to receive their randomized treatment in a blinded manner for the remainder of the planned 96 weeks of treatment and the follow-up phase.

Final – 22November2011 CONFIDENTIAL Page 13 of 30

The Week 24 analysis will be treated as an interim analysis with regard to the blinding and data handling. Since the primary efficacy analysis is conducted once at the Week 24 time point, no multiplicity adjustment will be used for the interim analysis.

### 3.6.2 Final Analysis

After all subjects have completed the planned 96 weeks of blinded study treatment and the subsequent follow-up phase, the final analysis for the clinical study report will be completed. At this time, the database will be frozen, and the treatment codes will be unblinded.

### 4 Analysis Sets

### 4.1 Safety Analysis Set

All subjects who are randomized and administered at least one dose of double-blind study medication will be included in the Safety Analysis Set. The safety analysis set will be used in safety analysis detailed in Section 9. All analyses using the safety analysis set will be analyzed according to treatment received.

### 4.2 Full Analysis Set

The full analysis set (FAS) will include all subjects in the safety analysis set who have a baseline and at least one post-baseline HbA1c measurement. The full analysis set will be used in efficacy analysis detailed in Section 7. All analyses of the full analysis set will be based on randomly assigned treatment.

## 4.3 Per Protocol Analysis Set

The Per Protocol Analysis set will include all subjects in the full analysis set who meet the study inclusion requirements and who have no major protocol deviations that would affect the validity of the efficacy measurements. The definition of major protocol deviations that would result the subject being excluded from the per protocol analysis set is detailed in Section 5.1.

The per protocol analysis set will be used in sensitivity efficacy analyses detailed in Section 7.3.3. All analyses using the per protocol analysis set will be based on randomly assigned treatment.

## 4.4 Deviations from Assigned Treatment

If a subject's actual treatment deviates from the randomly assigned treatment, the extent of the deviation and the type of data being analyzed will be considered in deciding how to assign the subject for analysis.

- If a subject takes the unassigned study medication for only part of the study, the subject will be analyzed based on the randomized treatment assignment for both safety and efficacy.
- If a subject takes the unassigned study medication for the entire study, the subject will be analyzed based on the treatment actually taken for safety analyses. However, the subject will be analyzed according to randomized treatment for efficacy per the intent-to-treat principle.

### 5 General Consideration for Data Analyses

Statistical analyses and summaries of safety and tolerability will be performed using SAS® software version 9.2 or later (SAS Institute, Cary, NC). In all cases, statistical testing and confidence intervals will be two-tailed and significance will be judged at the  $\alpha$ =0.05 level.

#### **5.1 Protocol Deviations**

Subject compliance to the protocol will be evaluated prior to unblinding the study and subjects with major protocol deviations will be identified. Specific criteria for what constitutes a major protocol deviation will be determined by the study team. The following criteria will be considered:

- Failure to meet key inclusion/exclusion criteria
- Use of prohibited concomitant medications
- Noncompliance with the study medication dosing schedule

Protocol deviations will be tracked by the clinical team using TrialWatch on an on-going basis and will be listed by subject. A table summary by treatment group and listing of major protocol deviations will be presented by subject for all randomized subjects.

## 5.2 Multiple Comparisons and Multiplicity

There is a single primary endpoint in this study and no correction for multiple comparisons is needed. All other secondary and exploratory analyses which do not qualify for formal statistical testing will not be corrected for multiplicity, and will have results presented with confidence intervals and nominal p-values.

## 5.3 Missing Data Algorithm

Final – 22November 2011 CONFIDENTIAL Page 15 of 30

Imputation of partial or missing dates for the determination of prior/concomitant medication status is addressed in Section 6.4 of this SAP. Imputation of partial or missing dates for the determination of treatment-emergence of adverse events, and handling of missing adverse event data related to event severity or relationship to study drug, are addressed in Section 9.1.

Subjects who discontinue from the study early will not be replaced. For some analyses, the last non-missing observation for a subject may be carried forward (LOCF).

#### 5.3.1 Last Observation Carried Forward

Imputation for missing observations will be applied to selected efficacy endpoints by using the last observation carried forward method. For subjects who withdraw from the study, the last valid observation recorded on treatment (scheduled or unscheduled) will be carried forward to all remaining visits. Also, for subjects in efficacy analyses who had missing observations prior to their last observation on treatment, the closest previous non-missing on-treatment observation will be carried forward to missing visits. If a subject had missing observation(s) immediately after baseline, the baseline observation will not be carried forward and the visit(s) will be left as missing.

In general, the LOCF method will be used for all efficacy endpoints that are evaluated at or before Week 24. Beyond Week 24, all analyses will not impute any missing data; this non-imputation method will be referred to as the observed case (OC). The descriptive summaries of endpoints by study medication group will include the count of missing values at each visit. The detail of which analysis utilizes LOCF algorithm is available in Section 7.

It is expected that 24 weeks of treatment is required to obtain the full treatment effect; shorter treatment periods may result in the observation of only a partial (smaller) treatment effect. Therefore, assuming that subject discontinuation of study drug or early termination from study will occur equally and at random in both treatment groups and in each stratum, this LOCF imputation approach is expected to provide a statistically conservative estimate for the treatment effect.

#### 5.3.2 Post-rescue Measurements

For subjects who are rescued for hyperglycemia, their post-rescue measurements of efficacy parameters will be handled in the same manner as missing values for the efficacy analyses. Post-rescue measurements of efficacy parameters may be included in limited exploratory analyses.

Post-rescue measurements of safety parameters will be included in analyses without any special handling.

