3.2 Rationale for Study Design and Control Group

THR-1442-C-418 is designed to evaluate the efficacy of EGT0001442 in the treatment of patients with T2DM. A randomized, double-blind study is the most suitable design and placebo is the appropriate control to evaluate a new agent in diabetic subjects. Diet and exercise counseling during the entire study will be provided to all participating subjects to reduce risks of worsening diabetic conditions. Monitoring plan based on SMBG, FPG, and HbA1c measurements as well as criteria to initiate rescue medications are included in the protocol to prevent prolonged hyperglycemia.

Results from published data in individuals with genetic mutations in the gene encoding SGLT2, subjects that have been treated with other SGLT2 inhibitors, and from previous clinical studies in healthy or diabetic subjects treated with EGT0001442 indicate that the risk of induced hypoglycemia as a consequence of the loss of SGLT2 activity should be minimal.

Reduction in HbA1c directly reflects improvement in glycemic control and is considered a well validated surrogate for the long-term microvascular complications of diabetes mellitus. Results from study THR-1442-C-402 demonstrated that 4 weeks of treatment resulted with a dose dependent reduction of 24 – 42 mg/dL FPG in subjects receiving EGT0001442 5 – 50 mg per day. Thirty (30) mg/ day of EGT0001442 dosage was chosen in the proposed study based on the near saturation of UGE and FPG decrease in previous clinical studies in healthy or diabetic subjects. Clinical data in the previous studies indicated that 30 mg/day EGT0001442 is well tolerated.

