5.2 Treatments Administered

Study drug will be provided to the pharmacist in bottles of 45 tablets per bottle. Individual bottles of placebo will be provided for the run-in portion of the study. For the first 24 weeks of the study, subject kits will be provided and each kit will contain 4 bottles containing 45 tablets per bottle. For study weeks 25 - 96, subject kits will contain 2 bottles of 45 tablets. Study drug, EGT0001442 10, 15, or 20 mg tablets or matching placebo, will be dispensed by the pharmacy or designated study staff every 6 - 12 weeks. There will be no intra-subject dose escalation or back-titration.

Subjects who require rescue medication due to hyperglycemia will receive standard care for treating type 2 diabetes in addition to the study drug. The pharmacist will dispense the medications per investigator's prescription.

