### Table 14.3-1.7

Treatment Emergent Adverse Events Leading to Treatment Discontinuation (Safety Analysis Set)

See Table 14.3-1.1 for layout. Use footnotes below.

Note: For each level of summarization, a subject is counted once if the subject reported one or more events.

Percentages are based on the number of subjects in each treatment group. The system organ class (SOC) and preferred term within the SOC are presented by decreasing frequency of incidence for all treatment groups combined.

Source Data: Listing 16.2-8.1

Table 14.3-1.8

Treatment Emergent Hypoglycemic Events by Severity and Intervention (Safety Analysis Set)

	EGT0001442 (N=xxx)	Placebo (N=xxx)	Total (N=xxx)
Total Number of Events	xx	xx	xx
Number of Subjects With at Least One Event	xx (xx.x%)	xx (xx.x%)	xx (xx.x%)
Severity			
Severe	xx (xx.x%)	xx (xx.x%)	xx (xx.x%)
Documented Symptomatic	xx (xx.x%)	xx (xx.x%)	xx (xx.x%)
Asymptomatic	xx (xx.x%)	xx (xx.x%)	xx (xx.x%)
Probable Symptomatic	xx (xx.x%)	xx (xx.x%)	xx (xx.x%)
Relative	xx (xx.x%)	xx (xx.x%)	xx (xx.x%)
Not Applicable	xx (xx.x%)	xx (xx.x%)	xx (xx.x%)
Missing	xx (xx.x%)	xx (xx.x%)	xx (xx.x%)
Intervention [1]			
Extensive	xx (xx.x%)	xx (xx.x%)	xx (xx.x%)
Immediate	xx (xx.x%)	xx (xx.x%)	xx (xx.x%)
Minor	xx (xx.x%)	xx (xx.x%)	xx (xx.x%)
None	xx (xx.x%)	xx (xx.x%)	xx (xx.x%)
Missing	xx (xx.x%)	xx (xx.x%)	xx (xx.x%)

Note: For each level of summarization, a subject is counted in all severity or intervention categories if the subject reported one or more events. Percentages are based on the number of subjects in each treatment group.

Source Data: Listing 16.2-8.1

 Extensive = glucose injection/infusion/glucagon; Immediate = glucose drinks or supplements; Minor = administered sugary drinks or sweets; None = no intervention.

Table 14.3-2.1 Change from Baseline in Hematology (Safety Analysis Set)

	EGT00	01442	Plac	cebo
	(N=xxx)		(N=2	xxx)
		Change from		Change from
	Result	Baseline	Result	Baseline
Lab Test #1 (unit)				
Baseline				
n	xxx		xxx	
Mean (SD)	xx.x (xx.xx)		xx.x (xx.xx)	
Median	xx.x		xx.x	
Min, Max	xx, xx		xx, xx	
Week 2				
n	xxx	xxx	xxx	xxx
Mean (SD)	xx.x (xx.xx)	xx.x (xx.xx)	xx.x (xx.xx)	xx.x (xx.xx)
Median	xx.x	xx.x	xx.x	xx.x
Min, Max	xx, xx	xx, xx	xx, xx	xx, xx

Note: Baseline is defined as the last available assessment on or prior to the first dose of study medication. Source Data: Listing 16.2-9.1

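### Hypoglycaemia is tabulated by arm over the whole study with no split at added antidiabetic therapy, so an excess on study drug can be masked

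*SAP*

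**What the plan says.** **Handling rule.** SAP 5.3.2: "Post-rescue measurements of safety parameters will be included in analyses without any special handling". The same section treats post-rescue efficacy values as missing and gives no reason for the difference.

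**What is counted.** Under SAP 9.1.1 an event is treatment-emergent if it starts on or after first dose. There is no cut at rescue or at Week 24. Starting an added drug does not change a subject's arm (SAP 4.1, 4.4).

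**Where hypoglycaemia appears.** It is an adverse event of special interest (SAP 9.1.3). Table 14.3-1.8, "Treatment Emergent Hypoglycemic Events by Severity and Intervention", gives one count per arm. Hypoglycaemia can also appear by arm as a preferred term in Tables 14.3-1.2 to 14.3-1.7. None of these tables shows rescue status, period or exposure time. The hypoglycaemia listings (14.3-5.1, 14.3-6.1, 16.2-8.2) carry onset dates but no rescue flag; a post-rescue column exists only in the efficacy listings 16.2-7.1 to 16.2-7.5.

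**Added therapy.** Rescued subjects "will receive standard care for treating type 2 diabetes in addition to the study drug" (Protocol 5.2). Protocol 3.1 ties this to glucose in the first 24 weeks and to HbA1c in the extension. SAP 3.4 releases HbA1c values once all subjects have completed Week 24, partly to assess rescue. On the agents, the Glycemic Control text of Protocol 3.1 refers to oral therapy in the extension; elsewhere 3.1 and 5.1.3 refer more broadly to approved medication and standard of care. No class is named.

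**Prior expectation.** Protocol 3.2 says "the risk of induced hypoglycemia as a consequence of the loss of SGLT2 activity should be minimal". Protocol 1.1.2 reports no hypoglycaemia in the 28-day phase 2 study.

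**The concern.** Safety is a secondary objective, and the cited clinical experience in diabetic subjects lasted 28 days, so this 96-week trial is the longer evidence on hypoglycaemia. The table that carries that evidence mixes two sources: events on study drug or placebo alone, and events after a further glucose-lowering drug has been added.

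If the second source is larger on placebo, it raises the placebo rate and pulls the comparison towards no excess. A reader of the pooled table could not tell a drug with no hypoglycaemia signal from one whose signal is offset by added therapy in the other arm.

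**Working it through.** **1. The plan's own figure.** There is none for hypoglycaemia or rescue. The nearest is the primary sample size, which supplies the effect assumption used in step 2. Inputs (SAP 3.5): for the active arm, "The mean change from baseline to Week 24 in HbA1c in the active dose group will be approximately -0.4" percentage points; for placebo, no material change; SD 1.0 percentage points in each arm; and for alpha, "the two-sided significance level for the hypothesis is 0.05". With 90% power:

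n per arm = 2 × (1.960 + 1.282)² × 1.0² / 0.4² = 131.3, so 132 (normal); the t version gives 132.3, so 133.

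The SAP states 133 and Protocol 9.2 states 131 (power 90.4% and 89.9% by the normal formula). The figure reproduces. It says nothing about hypoglycaemia.

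**2. Does imbalance follow from the plan?** Glucose and HbA1c trigger added therapy in both arms, and the plan assumes active lowers HbA1c while placebo does not. More added therapy on placebo is therefore likely, although neither document says so or gives a rate.

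**3. How far could pooling move the comparison?** Every input here is an assumption. Let p be the 96-week risk without added therapy, r the share given added therapy and h the extra risk it brings, taken as independent of p.

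Arm risk = 1 − (1 − p)(1 − r·h)

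Take p = 2% placebo and 6% drug: true difference 4.0 points, risk ratio (RR) 3.00. Example with r = 30%/15% (placebo/drug) and h = 10%:
- placebo: 1 − 0.98 × 0.970 = 4.9%
- drug: 1 − 0.94 × 0.985 = 7.4%
- difference 2.5 points, RR 1.50

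| r placebo/drug | h | Difference (points) | RR |
|---|---|---|---|
| any | 0 | 4.0 | 3.00 |
| 20%/10% | 5% | 3.5 | 2.17 |
| 20%/10% | 10% | 3.0 | 1.75 |
| 30%/15% | 5% | 3.2 | 1.93 |
| 30%/15% | 10% | 2.5 | 1.50 |
| 30%/15% | 20% | 0.9 | 1.12 |
| 40%/20% | 20% | −0.1 | 0.99 |
| 50%/20% | 20% | −2.0 | 0.83 |
| 20%/20% | 20% | 3.8 | 1.65 |

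The last row shows that with equal rescue the difference barely moves, though the ratio is diluted.

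**4. Break-even.** The excess disappears when 0.04 = h(0.98·r_placebo − 0.94·r_drug). For 30%/15%, h = 0.04/0.153 = 26%; for 40%/20%, 0.04/0.204 = 20%; for 50%/20%, 0.04/0.302 = 13%.

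**5. Can the direction change?** Yes. If study drug doubles the added agents' effect (30%/15%, h = 10% on placebo and 20% on drug), drug risk is 1 − 0.94 × 0.97 = 8.8%. The pooled difference is then 3.9 points, RR 1.79; at triple the effect it is 5.3 points, RR 2.07. So masking is possible, not assured.

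**6. Why crude pre-rescue percentages are not enough.** Suppose added therapy starts on average halfway through 96 weeks. With 30%/15%, mean follow-up before it is 96 × (1 − 0.30/2) = 81.6 weeks on placebo and 96 × (1 − 0.15/2) = 88.8 weeks on drug. The longer drug-arm exposure alone inflates a crude ratio by about 88.8/81.6 = 1.09.

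**The case against.** **Keeping all safety data is legitimate.** It answers what happens under assigned treatment plus usual care. This stands, and it is why the all-events table should remain.

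**No inference is at stake, and events may be few.** This also stands. No hypoglycaemia test is planned. With 150 per arm, even 4% against 2% is 6 against 3 subjects (Fisher p = 0.50, ratio interval about 0.5 to 7.8). A pre-rescue table would not reliably establish an excess of that size. Its value is descriptive.

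**The split can be rebuilt from listings.** Partly true. Event onset dates, medication start dates and a rescue flag are all listed, and Table 14.1-3.4 gives time of first rescue by arm. But nothing links them, and an unplanned reconstruction after unblinding is weaker than a pre-specified table. The Week 24 analysis (SAP 3.6.1) is described as limited, and its safety content is not specified.

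**Stronger readings that a reader might infer, and that the documents do not support:**
- That 14.3-1.8 is the only by-arm view of hypoglycaemia. It is the only dedicated one; the general TEAE tables also show the term.
- That added therapy will include insulin or secretagogues. The protocol's introduction lists these as disease background, not as rescue agents, and one passage limits the extension to oral therapy.
- That the SAP contradicts its own reason for excluding post-rescue efficacy values. It states no reason. What can be said is that SAP 7.2 presents efficacy summaries both with and without post-rescue values, and hypoglycaemia gets only the inclusive form.

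**Conclusion.** The concern holds as a reporting gap. A stated rule, applied through an unsplit table, can mask a hypoglycaemia excess on study drug. Two conditions are needed: added therapy is more frequent on placebo, which is likely on the plan's own effect assumption, and the added agents carry hypoglycaemia risk, which the documents leave open.

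The size is unknown. In the illustration a 4.0-point excess becomes anything from 4.0 points (no added risk) to 2.5 points (30%/15%, 10% added risk) to −2.0 points (50%/20%, 20% added risk). A reader might infer that pooling will hide an excess or reverse its sign. The documents do not support that: reversal needs high, unequal rescue and a high added risk, and amplification by study drug would push the other way. The phase 2 report of no hypoglycaemia in 28 days gives no sign of an excess, but it is too short to settle 96 weeks.

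This is worth correcting because the remedy is cheap. It does not affect the primary analysis.

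**What to change.** 1. Keep Table 14.3-1.8 unchanged as the all-data summary.
2. Add a descriptive version limited to events with onset before the first antidiabetic medication started after first dose, whether recorded as rescue or as an extension add-on. Censor exposure at that date and show exposure-adjusted rates per arm beside n (%).
3. Add a version for Weeks 0-24. It still contains rescued subjects, so it complements item 2 and does not replace it.
4. Amend SAP 5.3.2 to say that hypoglycaemia is reported with and without events after added therapy. Note there that the pre-rescue version has less follow-up and censors on a post-randomisation event, so it is supplementary.
5. State a date rule for item 2: SAP 6.4 places a completely missing medication start date before first dose, so such a drug would not trigger the cut.

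**Cost.** A short SAP amendment, two repeat table shells and one exposure derivation. Event onset dates, medication start dates and the antidiabetic and rescue flags are already in the listings (16.2-8.2, 16.2-5.1). No new data are collected and patient management does not change. The price is a pre-rescue table with less exposure, more of it lost on placebo if rescue is more frequent there. This is why it needs rates and must sit beside the all-events table.
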